6.2 Secondary Endpoint - Safety

The study's secondary safety endpoints are:

- Device-related* death within 48 hours (\pm 8 hours) of the procedure
- Major bleeding within 48 hours (\pm 8 hours) of the procedure
- Device-related* Clinical deterioration within 48 hours (\pm 8 hours) of the procedure
- Device-related* Pulmonary vascular injury within 48 hours (\pm 8 hours) of the procedure
- Cardiac injury within 48 hours (\pm 8 hours) of the procedure
- Mortality due to any cause within 30 days (\pm 3 days) of the procedure
- Device-related* serious adverse events within 30 days (\pm 3 days) of the procedure
- Symptomatic recurrence of embolism within 30 days (\pm 3 days) of the procedure

**Adverse Events judged as possibly related, probably related or with causal relationship to Vertex Pulmonary Embolectomy System will be considered device-related.*

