7. ENDPOINT DEFINITIONS

7.1 Device-Related Death

Device-related death is defined as any death directly related to the device not performing as expected. Device-related death could include death from:

- Vascular or cardiovascular injury
- Device deficiency
- Device-induced cardiac arrhythmia
- Worsening pulmonary or right heart function (exclusive of worsening from recurrent PE)

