7.3 Recurrent PE

The Vertex Pulmonary Embolectomy System is designed to mechanically remove emboli and restore blood flow through the pulmonary arteries in patients experiencing acute PE. The goal in using this device is not 100% removal of clot but rather to remove enough clot to make a clinically significant difference in the patient. As this is a mechanical procedure where all, patients will not receive any concomitant thrombolytic therapy, new recurrence is not unexpected.

Recurrence in this study is defined as a symptomatic worsening from baseline of the embolism that was successfully treated with the index procedure. Based on the International Society on Thrombosis and Hemostasis (ISTH) guidance, "successful" means a clear clinical improvement of Subject symptoms and signs.⁴³ Symptomatic recurrent PE will be confirmed by CTA. "Symptomatic" means clinical symptoms and/or signs such as chest pains, dyspnea, hemoptysis, palpitations, or tachycardia.

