9. STUDY VISITS

The table of study procedures and follow up visits is presented below in Table 4. All scheduled exams listed in Table 4 must be performed at the designated time point and the results documented in the EDC. The following table details the clinical and laboratory procedures required from Screening through the 30-day follow-up visit. The majority of these tests and procedures are considered standard of care for all patients under treatment of clinically significant PE.

Table 4: Schedule of Assessments

Assessment/Method	Screening/ Baseline	Procedure Day 0	Post- Procedure	48 (± 8) Hours* Follow-up Day 2	30 (± 3) Days Follow-up Day 30~ (Clinic or Phone visit)
Informed Consent	X				
Demographics	X				
Medical/Surgical History	X				
Physical Examination/Vitals	X	X ⁺	X	X	
Blood Labs (Hematocrit, Platelets, Sr creatinine, INR, BNP, Troponin, Serum lactate)	X		X		
Room Air SpO2	X			X	
mMRC dyspnea score	X			X	X
CT Angiography	X			X	
Echocardiogram	X			X	
Right heart Catheterization (Invasive Hemodynamic Assessment)		X	X		
Pulmonary Aspiration Thrombectomy		X			
Pregnancy Test	X ⁼				
Major Trauma Injury Severity Score (ISS),	X []]				
Concomitant Medications [#]	X		X	X	X
Assessment of AEs/DDs	X [^]	X	X	X	X

*or discharge; whichever occurs first = Only for females of childbearing age only who are not surgically sterilized] As applicable for subjects suspected of enduring trauma + Vitals only #Relevant concomitant medications to be documented for the study are anticoagulants, vasopressors, thrombolytics used, and all other medications given for AEs and SAEs during the study ~ 30-day visit can be completed onsite or via televisit ^ Any adverse event/device deficiency occurring since subject signed ICF will be recorded in the subject's CRF. Note: Any medical condition that is present at the time that the subject is screened will be considered as baseline and not reported as an adverse event further in the study. However, if that subject's condition deteriorates at any time during the study, it will be recorded as an AE.
					

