9.3 Follow Up Visits

9.3.1 48-Hour Follow-up Evaluation – Day 2: (\pm 8 Hours or discharge)

The following assessments will be performed at this clinic visit:

- Physical examination and vitals
- Room Air SpO₂
- mMRC dyspnea score
- Repeat CTA and Echocardiogram consistent with baseline imaging study
- Adjunctive Treatment
- Record adverse events, as applicable
- Record concomitant medications
- Record clinical investigation plan deviations

9.3.2 30-Day Follow-up Evaluation- Day 30: (\pm 3 Days) (clinic or phone visit)

The following assessments will be performed at this visit:

- mMRC dyspnea score
- 30-day readmission rate
- PE recurrence rate
- Record adverse events, as applicable

- Record concomitant medications
- Record clinical investigation plan deviations
- Complete study Exit form (CRF)

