9.5 Unscheduled Visit

Unscheduled assessments should be done as clinically indicated and corresponding data must be documented on the case report forms and submitted to the Sponsor.

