12.1 Imaging Core Laboratory

Medical Metrics Inc is the Core Lab designated for the SPIRARE I Clinical Study. The objectives of the Core Lab are to provide an unbiased assessment of the RV/LV ratio.

For each Subject treated with the Vertex Pulmonary Embolectomy System, the investigational site will be instructed to follow a standard procedure developed by the Core Lab for obtaining study specific angiographic images. CT imaging studies will be obtained at baseline and 48 hours (± 8 hours) follow-up.

Images will be sent directly from the site to the Core Lab. Core Lab definitions and procedures will be documented in the Core Lab Manual of Operations (MOP) and CRFs.

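### Section 7.3 accepts only CTA as confirmation of recurrent PE, so, read literally, a recurrence proven at autopsy or shown by other imaging is left out of the 30-day rate

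*Combined protocol and SAP*

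**What the plan says.** - **Endpoint.** Section 6.2 lists "Symptomatic recurrence of embolism within 30 days" (with a window of 3 days either side) among the secondary safety endpoints.
- **Confirmation.** Section 7.3 states: "Symptomatic recurrent PE will be confirmed by CTA". It names no other test, does not mention autopsy, and has no category for a probable or suspected event. It also limits recurrence to worsening of an embolism that the index procedure treated successfully.
- **Scheduled imaging.** Section 12.1 says "CT imaging studies will be obtained at baseline and 48 hours" (with an 8-hour window). Table 4 marks the same two CTA time points and no later one.
- **Day 30.** Section 9.3.2 lists "PE recurrence rate" among the Day 30 items and no imaging. A footnote to Table 4 adds that the "30-day visit can be completed onsite or via televisit".
- **Unscheduled scans.** Section 9.5 says "Unscheduled assessments should be done as clinically indicated". It does not mention CTA or suspected recurrence.
- **Deaths.** Section 11.5 asks sites for the death certificate and, where there is one, the autopsy report.
- **Device-related death.** Section 7.1 introduces its causes with "Device-related death could include death from". One listed cause is "Worsening pulmonary or right heart function (exclusive of worsening from recurrent PE"). Under sections 6.1 and 6.2 this endpoint covers 48 hours, with an 8-hour window.
- **Analysis.** Section 13.2 summarises observed data descriptively and gives no rule for an unconfirmed event.

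**The concern.** The endpoint runs for 30 days, but its only named confirmation is a scan that the schedule provides for about the first two. After that, a CTA depends on clinical judgement and on the patient living long enough to have one. Three kinds of event may therefore be handled badly:

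1. a fatal PE before any scan, even when autopsy proves it;
2. a recurrence diagnosed by another imaging test;
3. symptoms reported at a remote Day 30 contact and never scanned.

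The first two are true recurrences that the literal definition does not count. The third has no scoring rule. A confirmation requirement properly screens out symptoms that are not PE. Among true recurrences, however, it can only remove events, so the error in the rate runs downward. In a study of at most 10 subjects, one event decides whether the report shows any recurrence at all.

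**Working it through.** **No figure to reproduce.** The plan states no recurrence rate, and the maximum of 10 subjects (section 2.1) comes from no calculation. The check compares sections and then measures the effect of one missed event.

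**Where each type of event would be recorded**

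| Event within 30 days | Recurrence under 7.3 | Elsewhere |
|---|---|---|
| Symptoms, CTA positive | Counted | AE/SAE reporting |
| Symptoms, other imaging positive | Not counted, read literally | Device-related SAE, if serious and at least possibly related |
| Death, PE proven at autopsy, no CTA | Not counted, read literally | All-cause mortality; device-related SAE if at least possibly related |
| Symptoms or death, PE suspected, no test | No rule | As above, according to outcome |

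The bleeding definition in section 7.2.2 handles the same problem differently. It counts BARC 5a, probable fatal bleeding, without autopsy or imaging proof. The plan therefore accepts clinical suspicion for a fatal bleed, but for a fatal recurrence it does not name even autopsy proof, although section 11.5 already requests the autopsy report.

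**Effect of one missed event**

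Assume a denominator of n = 10. Section 13.1 adds procedural screen failures to the safety analysis, which could make it somewhat larger. Exact (Clopper-Pearson) 95% limits:

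- 0/10: upper limit 1 − 0.025^(1/10) = 1 − 0.6915 = 0.3085, so 0% (0% to 30.8%).
- 1/10: lower limit 1 − 0.975^(1/10) = 0.0025; upper limit, the 97.5% quantile of Beta(2, 9), = 0.445, so 10% (0.3% to 44.5%).

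Each missed event is worth 1/10 = 10 percentage points.

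**Chance that the report shows any recurrence**

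Let p be the true 30-day recurrence rate and s the share of recurrences confirmed by CTA. Neither is in the documents; the values below are assumptions. The chance of at least one scored event is 1 − (1 − p·s)^10.

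| Assumed p | s = 1 | s = 0.75 | s = 0.5 |
|---|---|---|---|
| 2% | 18.3% | 14.0% | 9.6% |
| 5% | 40.1% | 31.8% | 22.4% |
| 10% | 65.1% | 54.1% | 40.1% |

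For example, with p = 5% and s = 0.5: 1 − 0.975^10 = 0.224.

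**The case against.** The strongest reply is that the endpoint is symptomatic recurrence, so a scan prompted by symptoms suits it and no routine late CTA is needed. Section 9.5 allows such scans, and the sentence in 7.3 can be read as an instruction to scan. Day 30 also records readmissions, so a hospital work-up would come to light even by phone. This stands as far as it goes: the gap concerns scheduled or explicitly required CTA, not permitted CTA. It does not help when the patient dies first or is diagnosed by another test.

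Contrast problems add little. Section 2.10 excludes creatinine above 1.8 mg/dL and contrast anaphylaxis that cannot be pretreated, and the schedule already gives every subject two CTAs. The study is also small and descriptive, so an individual case can be narrated in the report. That limits the harm but does not say how the case enters the rate.

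Three stronger readings are tempting, and the documents do not support them.

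- *A fatal recurrence is barred from device-related death.* The list in 7.1 is open, the exclusion qualifies one item in it, and the endpoint ends at 48 (±8) hours. Later deaths fall outside it whatever their cause. An event that 7.3 does not recognise as recurrence is also not clearly caught by an exclusion for recurrent PE. Only early deaths remain unclear.
- *A fatal recurrence survives only in all-cause mortality.* Section 6.2 also counts device-related SAEs to 30 days and includes possibly related events. Section 11.4 classifies cases whose relatedness cannot be assessed as possible. Within 48 hours, device-related clinical deterioration also enters the primary composite.
- *A death in the study is about as likely as not.* The 6.1% and 8.2% intermediate-risk mortality in section 1.3.4 give 1 − 0.939^10 = 47% and 1 − 0.918^10 = 57%. The 800-patient thrombectomy registry in Table 2 reports 0.8% at 30 days, which gives 1 − 0.992^10 = 7.7%. The share of deaths due to recurrent PE is not stated, so none of these figures measures the problem.

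**Conclusion.** The point holds as a gap in an endpoint definition. Section 7.3 names one acceptable confirmation for a 30-day safety endpoint, and no CTA is scheduled or explicitly required after 48 hours or discharge. Taken literally, it leaves out recurrences proven at autopsy or by other imaging, and it gives no rule for suspected cases with no test. A reader might infer that the plan scores an untested case as no recurrence, but no section says so.

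The serious events themselves are not necessarily lost, because other safety endpoints can capture them. What is lost is their attribution to recurrence, and the recurrence rate would then be too low. One missed event in 10 moves the result from 10% (0.3% to 44.5%) to 0% (0% to 30.8%). This rests on a denominator of 10 and on at least one recurrence not confirmed by CTA; the documents give no basis for how likely that is. As this is a secondary endpoint in a descriptive study, the point is modest, but it is worth correcting because the correction is only wording.

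**What to change.** 1. In section 7.3, accept as confirmation CTA, other diagnostic imaging already done for clinical care, or autopsy.
2. Add a separate category, *suspected, unconfirmed*, for symptomatic cases and deaths in which recurrence is suspected but not confirmed. In section 13.2, state that the recurrence rate is reported with and without this category.
3. Do not count every death in which PE cannot be excluded as a recurrence. That would include deaths from the index embolus, contrary to the requirement in 7.3 that the embolism was successfully treated, and would replace a downward bias with an upward one.
4. Reconcile the recurrent-PE exclusion in 7.1 with 7.3, so that a death within 48 hours attributed to recurrence but without CTA has a stated classification.

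The cost is definition wording and a category to record unconfirmed cases. No extra scans are needed, and autopsy reports are already requested. The reported recurrence rate may come out slightly higher.

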7.4 Clinical Deterioration

Clinical deterioration is defined by hemodynamic or respiratory worsening and will include treatment-related events, such as;

- Unplanned endotracheal intubation,
- Unexpected requirement for mechanical ventilation,
- Arterial hypotension (>1 hour or requiring vasopressors) or shock,
- Cardiopulmonary resuscitation,
- Persistent worsening in oxygenation, and
- Emergency surgical embolectomy.

7.5 Pulmonary Vascular Injury

Pulmonary vascular injury is defined as perforation or injury of a major pulmonary arterial branch during the index procedure requiring intervention, including but not limited to blood transfusion, open or endovascular intervention, to avoid permanent injury.

7.6 Cardiac Injury

Cardiac injury is defined as any damage to the heart during the index procedure requiring intervention, including but not limited to blood transfusion, open or endovascular intervention, to avoid permanent injury.

8. STUDY PROCEDURES

8.1 Overview of Study Flow

Subjects presenting with acute PE will be evaluated by the Investigator, in accordance with their institutional practices, to establish an appropriate treatment plan based on the patient's medical condition and available diagnostic screening procedures prior to recruitment in the SPIRARE I Clinical Study. Informed Consent will be obtained prior to proceeding to the treatment suite. A representative overview of the study flow is shown in Figure 11.

[figure not shown]

Figure 11: Representative Study Flow from Screening to Discharge

9. STUDY VISITS

The table of study procedures and follow up visits is presented below in Table 4. All scheduled exams listed in Table 4 must be performed at the designated time point and the results documented in the EDC. The following table details the clinical and laboratory procedures required from Screening through the 30-day follow-up visit. The majority of these tests and procedures are considered standard of care for all patients under treatment of clinically significant PE.

Table 4: Schedule of Assessments

Assessment/Method	Screening/ Baseline	Procedure Day 0	Post- Procedure	48 (± 8) Hours* Follow-up Day 2	30 (± 3) Days Follow-up Day 30~ (Clinic or Phone visit)
Informed Consent	X				
Demographics	X				
Medical/Surgical History	X				
Physical Examination/Vitals	X	X ⁺	X	X	
Blood Labs (Hematocrit, Platelets, Sr creatinine, INR, BNP, Troponin, Serum lactate)	X		X		
Room Air SpO2	X			X	
mMRC dyspnea score	X			X	X
CT Angiography	X			X	
Echocardiogram	X			X	
Right heart Catheterization (Invasive Hemodynamic Assessment)		X	X		
Pulmonary Aspiration Thrombectomy		X			
Pregnancy Test	X ⁼				
Major Trauma Injury Severity Score (ISS),	X []]				
Concomitant Medications [#]	X		X	X	X
Assessment of AEs/DDs	X [^]	X	X	X	X

*or discharge; whichever occurs first = Only for females of childbearing age only who are not surgically sterilized] As applicable for subjects suspected of enduring trauma + Vitals only #Relevant concomitant medications to be documented for the study are anticoagulants, vasopressors, thrombolytics used, and all other medications given for AEs and SAEs during the study ~ 30-day visit can be completed onsite or via televisit ^ Any adverse event/device deficiency occurring since subject signed ICF will be recorded in the subject's CRF. Note: Any medical condition that is present at the time that the subject is screened will be considered as baseline and not reported as an adverse event further in the study. However, if that subject's condition deteriorates at any time during the study, it will be recorded as an AE.
					

9.1 Screening and Baseline Assessments

The following baseline assessments will be conducted at screening/baseline. Since most assessments are part of standard of care for acute PE, informed consent is not required prior to conducting these assessments.

1. Inclusion/Exclusion criteria
2. Demographics
3. Medical/Surgical History- Relevant medical and surgical history will be collected from all consented Subjects at the time of consent or prior to enrollment.
4. Physical Exam and Vital signs
5. CT Angiography
6. Echocardiogram
7. Right Heart Catheterization (Invasive Hemodynamic Assessment)
8. Laboratory - Blood tests are required for Subject inclusion/exclusion criteria evaluation. Study informed consent is not required in order to obtain blood tests as the required tests are a standard of care in assessing PE treatment. The following labs must be available to assess Subject eligibility for the study:
 - a. Hematocrit (NOTE: hematocrit required within 6 hours of index procedure)
 - b. Platelets
 - c. Serum creatinine
 - d. International normalized ratio (INR)
 - e. B-type natriuretic peptide (BNP)
 - f. Troponin
 - g. Serum Lactate
9. Room Air SpO₂
10. Major Trauma Injury Severity Score (ISS), as applicable
11. mMRC dyspnea score
12. Pregnancy Test
13. Concomitant Medications- relevant concomitant medication use during the study be documented at baseline, pre-procedure, procedure, and follow-up visits. Relevant medications for this study include *anticoagulants, vasopressors, thrombolytics used, and all other medications given for AEs and SAEs during the study.*

As part of the standard of care to treat acute PE, anticoagulation medication is administered to impede blood clotting and thrombolytic medication may be administered to dissolve blood clots. The specific dose and course of administration is at the discretion of the Investigator and will be recorded on the case report form (CRF).

Any adverse event/device deficiency occurring since subject signed ICF will be recorded in the subject's CRF. Any medical condition that is present at the time that the subject is screened will be considered as baseline and not reported as an adverse event further in the study. However, if that subject's condition deteriorates at any time during the study, it will be recorded as an AE.

9.1.1. Computed Tomography Angiography (CTA)

Following imaging assessments will be conducted at baseline. Given the importance of imaging to Subject assessment, before and during the study, the Sponsor will collaborate with participating centers to evaluate and optimize the quality of imaging and image transfer associated with the Study.

The Study requires a CTA be obtained for Subject screening to confirm pulmonary embolism, assess RV/LV dysfunction and determine the Modified Miller Score (MMS). The modified Miller index score is a quantitative tool used for anatomic quantification of thrombus burden and pulmonary arterial obstruction based on a computed tomographic angiogram. This will be measured by a qualified core laboratory. The modified Miller score (MMS) of 0–16 assigns an aggregate score to the affected segmental pulmonary arteries (nine on the right, seven on the left) occluded by thrombus. With increasing thrombus load in PE, there is CTA evidence of RV decompensation with an MMS threshold of 12. This suggests a “tipping point” beyond which RV decompensation is more likely to occur.

9.1.2 Echocardiogram

An echocardiogram will be conducted at Subject screening and at discharge or the 48-hour follow up (whichever occurs earlier). Please refer to the study imaging protocol for more details concerning the parameters of the echocardiogram.

9.1.3 Right Heart Catheterization

Once access is achieved, pulmonary artery systolic and mean pressures will be obtained and recorded prior to starting the Vertex Pulmonary Embolectomy System procedure. After the Vertex Catheter has been removed, a post-procedure invasive PA mean artery pressure and systolic pressure will be obtained. Cardiac Output, Cardiac Index and total pulmonary vascular resistance will be measured.

9.2 Procedure (Day 0)

The following assessments will be conducted during the procedure:

1. Vital Signs
2. Venous puncture for Vertex-Pulmonary Embolectomy Procedure
3. Right heart catheterization (pre-and post-procedure) for ruling out pulmonary hypertension and Invasive hemodynamic assessment- systolic and mean PA pressures. Cardiac Output, Cardiac Index and Total Pulmonary Vascular Resistance will be assessed
4. Vertex Pulmonary Embolectomy System Procedure: For procedural details please refer to section **Section 4** above. NOTE: Hematocrit requirement (< 28%) must be confirmed prior to index procedure.
5. Following data will be collected:
 - Procedure time
 - Thrombectomy time
 - Number of Devices used in Pulmonary Arteries
 - Use of Adjunctive treatment
 - Number of times pulmonic Valve re-crossed with the same device
 - Use of stiff guidewire
 - Number of aspirations, location
 - Fluoroscopy time
 - Radiation dosage
 - Contrast volume
6. Device Accountability
7. Concomitant medications (Pre procedure)
8. Adverse Events/Device Deficiencies
9. Clinical Investigation Plan Deviations

9.3 Follow Up Visits

9.3.1 48-Hour Follow-up Evaluation – Day 2: (\pm 8 Hours or discharge)

The following assessments will be performed at this clinic visit:

- Physical examination and vitals
- Room Air SpO₂
- mMRC dyspnea score
- Repeat CTA and Echocardiogram consistent with baseline imaging study
- Adjunctive Treatment
- Record adverse events, as applicable
- Record concomitant medications
- Record clinical investigation plan deviations

9.3.2 30-Day Follow-up Evaluation- Day 30: (\pm 3 Days) (clinic or phone visit)

The following assessments will be performed at this visit:

- mMRC dyspnea score
- 30-day readmission rate
- PE recurrence rate
- Record adverse events, as applicable

- Record concomitant medications
- Record clinical investigation plan deviations
- Complete study Exit form (CRF)

